## Background and purpose

As the mechanisms of action underlying commonly prescribed light-based therapies are still not fully understood, our study aims to investigate clinical and physiological changes on the surface of the eyes and eyelids using clinically and readily available instruments. Two light-based therapies commonly prescribed are intense pulsed light (IPL) and low-level light therapy (LLLT), often in combination (IPL+LLLT). While IPL+LLLT is becoming a more common treatment regimen worldwide, recent evidence has also shown that LLLT alone is more effective at alleviating dry eye signs and symptoms better than IPL (Giannaccare et al, 2023). The proposed study aims to investigate the short- and long-term morphological, functional and physiological changes in the eyelid skin and ocular surface following IPL+LLLT versus LLLT alone (with prior sham IPL) for the treatment of Meibomian gland dysfunction in dry eye disease. The findings from this study will contribute knowledge to eyecare practitioners regarding the cellular and molecular changes these treatments and strengthen clinical guidelines associated with the prescription of light-based therapies. Understanding the short- and long-term implications of these treatments will also enable eyecare practitioners to treat patients with a more evidence-based approach.

## Methods

### Materials and Instruments

[figure not shown]
#### 1. Light-based treatment protocol

The Eye-light unit (Espansione Group Ltd, Funo, Italy) was used to deliver the light-based therapies. Prior to the intense pulsed light therapy (IPL), the highest meiboscore of either eyelid and the Fitzpatrick skin grading was inputted into the unit system. This automatically calibrated the optical radiance output of the IPL. Table 1 details the exact output for each combination of settings.

**Table 1.** Optical radiance output of the intense pulsed light (IPL) therapy of the Eye-light unit (Espansione Group Ltd, Funo, Italy) according to inputted grading from the meiboscale and Fitzpatrick skin grading.

Pult Meiboscale	Fitzpatrick skin grading	Optical radiance output (J)
1	1	59
	2	59
	3	59
	4	59
2	1	60
	2	62
	3	62
	4	60
3	1	62
	2	66
	3	66
	4	64
4	1	65
	2	69
	3	69
	4	67

Figure 1 demonstrates the light-based treatment administration protocol used in this clinical trial for four treatment sessions.

**Figure 1.** Intense pulsed light (IPL) protocol with (A) sequential placements of treatment cartridge for the five different regions involved, and (B) sham IPL placement of a disconnected empty cartridge along the same five different regions on the contralateral side but with the working IPL cartridge pointed away from the patient's face to simulate a pulse. Low-level light therapy (LLLT) was then administered for 15 minutes (C) with placement of the mask consisting of a series of red light-emitting diodes (LEDs). These were conducted with the Eye-light unit (Espansione Group Ltd, Funo, Italy).

## 2. Ocular assessment schedules and details

The study was structured into multiple visits and all conducted at the Aston Dry Eye Clinic in Aston University, Birmingham, United Kingdom. Each visit lasted for about 1.5 hours, with the sequence of assessments detailed in Table 2:

- Visit 1: Screening ± First treatment session
- Visit 2 (2 to 3 weeks after Visit 1): Second treatment session
- Visit 3 (2 to 3 weeks after Visit 2): Third treatment session
- Visit 4 (2 to 3 weeks after Visit 3): Fourth and final treatment session
- Visit 5 (2 weeks after visit 4): First follow-up
- Visit 6 (3 months after visit 4): Second and final follow-up

**Table 2. The sequence of assessments for each visit**

Procedures	Visits					
	1	2	3	4	5	6
Screening with inclusion and exclusion criteria	✓					
OSDI, DEQ5 and adapted SANDE questionnaires	✓	✓	✓	✓	✓	✓
General medical and ocular history, and lifestyle questions	✓	✓	✓	✓	✓	✓
Visual acuity assessment	✓	✓	✓	✓	✓	✓
Oculus Keratograph 5M, Part 1	✓	✓	✓	✓	✓	✓

 
- Number of total and partial blinks in 30 s
 
- Tear meniscus height
 
- Non-invasive tear break up time
 
- Lipid layer pattern
 
- Bulbar and limbal hyperaemia grading
 
						
Laser Doppler flowmetry and multimodal spectroscopy at central lower eyelids	✓				✓	✓
Slit lamp biomicroscopy	✓	✓	✓	✓	✓	✓

 
- Telangiectasia grading
 
						

Procedures	Visits					
	1	2	3	4	5	6

 
- Number of blocked or capped Meibomian gland orifices
 
- Demodex detection (2 lashes randomly chosen on either lid and assessed with lateral traction method)
 
- Meibomian gland expression with Korb expressor
 
						
Oculus Keratograph 5M, Part 2	✓	✓	✓	✓	✓	✓

 
- Fluorescein sodium and lissamine green staining grading on ocular surface and lid wiper epitheliopathy
 
						
Meibography	✓				✓	✓
In-vivo corneal confocal microscopy	✓				✓	✓

The following provides further details the instrumentation or procedures involved:

**i. OSDI and DEQ5 questionnaires**

These are validated questionnaires used to assess the severity and frequency of the dry eye symptoms experienced by the participants. OSDI consists of 12 questions regarding the frequency of symptoms and impact of daily activities over the past week. The scores range from 0 to 100 [1]. The DEQ5 assesses the severity and frequency of the discomfort, dryness and wateriness during a typical day in the past month. The scores range from 0 to 22 [2]. The adapted SANDE questionnaire is a visual analogue scale quantifying the severity and frequency of dry eye symptoms for each eye separately from 0 to 100 [3]. These were self-administered by the patient on a printed A4 sheet of paper.

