## Statistical Analysis

Two-factor repeated measures analysis of variance (ANOVA) was used for statistical analysis to assess changes over time across the multiple visits between each treatment group. One-way repeated measures ANOVA was used to assess changes over time for overall measures including OSDI scores, DEQ-5 scores, visual acuity, and blink rate. The Greenhouse-Geisser correction was applied to the one-way and two-factor repeated measures ANOVA results to adjust for the lack of sphericity. Paired t-test for normally distributed data or Wilcoxon signed-rank test for non-normally distributed data was used to assess differences between the two treatment modalities within the same visit.

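### Does the one-month recall of DEQ-5 undermine its planned analysis over visits only two to three weeks apart?

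*Combined protocol and SAP*

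**What the plan says.** The section on the OSDI and DEQ5 questionnaires gives the two symptom scores different recall periods. For one, "The DEQ5 assesses the severity and frequency of the discomfort, dryness and wateriness during a typical day in the past month". For the other, "OSDI consists of 12 questions regarding the frequency of symptoms and impact of daily activities over the past week".

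The section on ocular assessment schedules lists "Visit 1: Screening ± First treatment session" and then "Visit 2 (2 to 3 weeks after Visit 1): Second treatment session". Visits 3 and 4 follow at the same spacing, Visit 5 comes two weeks after Visit 4, and Visit 6 comes three months after Visit 4. The row "OSDI, DEQ5 and adapted SANDE questionnaires" in Table 2 is ticked at all six visits.

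The Statistical Analysis section says: "One-way repeated measures ANOVA was used to assess changes over time for overall measures including OSDI scores, DEQ-5 scores, visual acuity, and blink rate". A Greenhouse-Geisser correction is applied. The only paired test named there, a paired t-test or Wilcoxon signed-rank test, "was used to assess differences between the two treatment modalities within the same visit". The section names no visit-to-visit contrast for any outcome, and no section discusses how a recall period overlaps the visit schedule.

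**The concern.** A score that looks back a month, taken two to three weeks after the first session, mixes treated and untreated days. If the DEQ-5 means are read visit by visit, three misreadings are possible:

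- The change by Visit 2 could be understated.
- A response complete after the first session could look like a further gain between Visits 2 and 3, while OSDI shows none. That could be credited to the second session.
- The recall window at Visit 5 reaches back past the fourth session. An apparent further improvement from Visit 5 to Visit 6 could therefore arise with no true change, or could hide slight waning.

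The Background and purpose section sets out to study both short-term and long-term changes, so the time course is of interest. The plan gives no rule for reading the individual visits.

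**Working it through.** The documents state no figure on this point, so there is none to reproduce.

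**Inputs**

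- Recall window W: one month for DEQ-5 (questionnaire section). Its length in days is not given; I take 30, with a range of 28 to 31. For OSDI it is 7 days.
- Gap g between treatment visits: 14 to 21 days (schedule section).
- First session at Visit 1 (assumption; the schedule makes it optional there).
- Days from the first session: Visit 2 = g, Visit 3 = 2g, Visit 4 = 3g, Visit 5 = 3g + 14.

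**Pre-treatment share of the window** = max(0, W − days since first session) / W

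| Visit | W = 30, g = 14 | W = 30, g = 21 | W = 28 to 31 |
|---|---|---|---|
| 2 | (30 − 14)/30 = 53.3% | (30 − 21)/30 = 30.0% | 25.0% to 54.8% |
| 3 | (30 − 28)/30 = 6.7% | 0% | 0% to 9.7% |
| 4 to 6 | 0% | 0% | 0% |

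For OSDI at Visit 2, 7 − 14 is negative, so there is no overlap.

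**If recent days weigh more.** With exponential weights of half-life h and W = 30, the share at Visit 2 is (2^(−g/h) − 2^(−30/h)) / (1 − 2^(−30/h)).

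- h = 14: (0.500 − 0.226)/0.774 = 35% for g = 14, and (0.354 − 0.226)/0.774 = 16% for g = 21.
- h = 7: 21% and 8%.

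**If the first session came 7 days after Visit 1** with later visits still timed from Visit 1 (assumption), the Visit 2 share is (30 − 7)/30 = 76.7% to (30 − 14)/30 = 53.3%. At Visit 3 it is (30 − 21)/30 = 30% for g = 14 and 0% for g = 21.

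**Effect on the visit means.** These use even averaging and hypothetical response shapes that the documents do not give. Values are shares of the full improvement, with W = 30.

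- Full response at the first session: Visit 2 shows 14/30 = 47% to 21/30 = 70%, Visit 3 shows 93% to 100%, and later visits show 100%. The apparent gain from Visit 2 to Visit 3 is 30% to 47%, where the true gain is zero.
- Equal gain of 0.25 per session: Visit 5 shows (2 × 0.50 + 14 × 0.75 + 14 × 1)/30 = 25.5/30 = 85% for g = 14, and (16 × 0.75 + 14 × 1)/30 = 26/30 = 87% for g = 21. Visit 6 shows 100%, so 13% to 15% appears between Visits 5 and 6 with no true change.

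**Effect on the planned omnibus test.** Between-visit sum of squares = Σy² − (Σy)²/6 over the six visit means. For the full response at the first session with g = 14 and W = 30:

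- Without overlap (0, 1, 1, 1, 1, 1): 5 − 25/6 = 0.833.
- With overlap (0, 0.467, 0.933, 1, 1, 1): 4.089 − 4.4²/6 = 0.862.
- Ratio: 0.862/0.833 = 1.03.

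Across both shapes, both gaps and W = 28 to 31, the ratio runs from 0.926 to 1.050. With the 7-day deferral (full response at the first session, g = 14, W = 30) the means are 0, 0.233, 0.700, 1, 1, 1 and the ratio is 0.966/0.833 = 1.16.

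**The case for a change.** The strongest case for acting is that an omnibus test says only that some visit differs. A significant result sends the reader to the visit means, and two symptom scores with different recall can then trace different courses from the same true response. The trial has a stated short-term aim, a clarifying sentence would cost almost nothing, and it would remove no data, visit or test.

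The overlap itself stands, and so does the caution about Visit 2. The case for changing the plan does not, for four reasons.

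- No section offers DEQ-5 at Visit 2 as an early-response endpoint, so the sentence would deny a claim that the plan never makes.
- DEQ-5 is one score per person. The light-based treatment protocol applies sham IPL to the opposite side of the same face, so this score cannot inform the comparison between treatments.
- The lack of named visit contrasts applies to every outcome and is not caused by DEQ-5 recall.
- Naming Visit 5 versus Visit 1 as a contrast to rely on would not settle the matter. Under equal gains per session, Visit 5 itself shows only 85% to 87% of the effect.

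The document is also written in the past tense, so a reading rule added now may be post hoc.

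**Conclusion.** The concern is arithmetically sound, but it is a matter of interpretation and no change to the plan follows. With a 30-day month and the first session at Visit 1, 30% to 53% of the DEQ-5 window at Visit 2 precedes treatment (25% to 55% for 28 to 31 days). How much of the score this affects is unknown, because the item asks for a typical day and not a 30-day mean. Weighting towards recent days lowers the share to 16% to 35% or to 8% to 21%, depending on the half-life.

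The planned ANOVA is little affected: its between-visit sum of squares is 0.93 to 1.05 of the undiluted value under the assumed shapes, or 1.16 in the deferred-start example. The Visit 1 to Visit 6 change compares a window wholly before treatment with one wholly after the fourth session, so it is unaffected. OSDI and the comparison between treatments are unaffected too.

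This is a gap that analysts fill sensibly when reporting. OSDI is the natural guide to the early course, and Visit 6 versus Visit 1 is the cleanest DEQ-5 change. Any use of Visit 5, against either Visit 1 or Visit 6, should bear in mind that its window spans the fourth session. Visit 3 deserves similar care if gaps were 14 days or the first session was deferred.

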**ii. Visual acuity assessment**

A standard vision chart mounted on the wall was used to assess high-contrast vision in logMAR units, calibrated at 3 m.

**iii. Oculus Keratograph 5M, Part 1 (Optikgerlite GmbH, Wetzlar, Germany)**

Number of total and partial blinks in 30 seconds, tear meniscus height measured using in-built calipers in the Oculus Keratograph 5M software (average of 3 measures), objective non-invasive tear break up time (average of 3 measures), subjective lipid layer pattern grading (1: Open meshwork; 2: Closed meshwork; 3: Wave pattern; 4: Amorphous pattern; 5: Colour fringe pattern) [4], and automated bulbar conjunctiva and limbal redness grading (0: none to 4: severe in 0.1 increments) were assessed using this instrument.

**iv. Laser Doppler flowmetry**

This is an instrument developed by the Aston Institute of Photonics Technology (Aston University, Birmingham, United Kingdom) which uses a small probe lightly touching the skin to analyse blood flow in small vessels [5, 6]. This was adapted and mounted on the slit lamp to assess the blood flow of the external cutaneous skin of the central lower eyelid of each side.

**v. Slit lamp biomicroscopy**

The number of blocked or plugged Meibomian gland orifices were assessed under white light of the slit lamp biomicroscope (CSO SL9900 Digital LED Slit Lamp, Worcestershire, United Kingdom). Subjective grading of telangiectasia in the lower lid

margin (from 0 signifying no telangiectasia, to 3 representing telangiectasia crossing orifices across  $\geq 50\%$  of the lid margin) was also conducted [7]. The number of eyelashes with any presence of Demodex mite around the base of the lashes were assessed by random selection of two lashes from each eyelid and using a lateral traction method as described previously [8]. Diagnostic Meibomian gland expression was conducted using a Meibomian Gland Evaluator (TearScience, North Carolina, United States) across five glands temporally, five glands centrally and five glands nasally. The expressibility and meibum quality were graded with the Pflugfelder scale (0: all 5 glands expressing; 1: 3 to 4 glands; 2: 1 to 2 glands; 3: no glands expressing) and Bron scale (0: clear fluid; 1: cloudy fluid; 2: cloudy particulate fluid; 3: inspissated), respectively [9], and averaged across the 15 glands assessed.

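### Cheap improvement: analyse the 0-15 count of expressing glands per eye, because the mean of three banded zone grades discards information

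*Combined protocol and SAP*

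**What the plan says.** Section 2.v describes diagnostic expression "across five glands temporally, five glands centrally and five glands nasally", which is three zones and 15 glands. Expressibility is graded 0 to 3, lower being better, with the bands "0: all 5 glands expressing; 1: 3 to 4 glands; 2: 1 to 2 glands; 3: no glands expressing". Meibum quality is graded on a separate 0 to 3 scale by type of fluid. Both are then "averaged across the 15 glands assessed".

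Table 2 schedules gland expression at all six visits. The Statistical Analysis section has no separate rule for this score, so the general methods apply. For change over time: "Two-factor repeated measures analysis of variance (ANOVA) was used for statistical analysis to assess changes over time across the multiple visits between each treatment group". Within a visit, a paired t-test or Wilcoxon signed-rank test is "used to assess differences between the two treatment modalities within the same visit". The documents name no primary outcome and give no sample size.

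**The concern.** The expressibility scale is a property of five glands together, so an average over 15 glands has to be an average of three zone grades. Giving each gland its zone's grade and averaging over 15 yields the same number. The bands hold one, two, two and one of the six possible zone counts. A change from 1 to 2 or from 3 to 4 glands in a zone is therefore invisible, while a change from 0 to 1, 2 to 3 or 4 to 5 moves the grade by a full point.

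Expressibility is a direct functional measure in a trial of Meibomian gland dysfunction. Both sides of the face receive LLLT and only one receives active IPL, so the between-side contrast is the added effect of IPL and may be small. A score that ignores some real gains makes such a contrast harder to detect. ANOVA and t-tests also suit a 0-15 count better than a mean of unequal ordinal bands.

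**Working it through.** The plan gives no figure for this score, so there is nothing of its own to reproduce.

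**Inputs from section 2.v.** Three zones of five glands. Zone grade g(k) for k expressing glands: g(5) = 0; g(4) = g(3) = 1; g(2) = g(1) = 2; g(0) = 3. Score = [g(k1) + g(k2) + g(k3)] / 3. Count = k1 + k2 + k3. There are 6 × 6 × 6 = 216 zone patterns.

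**One-gland gains.** Each zone has five possible steps (0→1, 1→2, 2→3, 3→4, 4→5), and the other two zones can be in any of 6 × 6 = 36 states. Total steps: 3 × 5 × 36 = 540. Steps that leave the grade unchanged (1→2 and 3→4): 3 × 2 × 36 = 216. Share: 216 / 540 = 40%, with all patterns weighted equally.

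**Counts covered by each score** (full enumeration):

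| Score | Expressing glands |
|---|---|
| 0.00 | 15 |
| 0.33 | 13-14 |
| 0.67 | 11-13 |
| 1.00 | 9-12 |
| 1.33 | 7-10 |
| 1.67 | 5-8 |
| 2.00 | 3-6 |
| 2.33 | 2-4 |
| 2.67 | 1-2 |
| 3.00 | 0 |

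For example, zones (3,3,3) and (4,4,4) both score (1+1+1)/3 = 1.00, with 9 and 12 glands. Zones (1,1,1) and (2,2,2) both score 2.00, with 3 and 6 glands. Three glands is the largest gain that can leave the score unchanged.

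**All ordered pairs in which the second pattern has more expressing glands:** 21,162.
- Score unchanged: 2,480 / 21,162 = 11.7%. Among gains of exactly three glands it is 50 of 3,431 (1.5%); for four or more it is none.
- Score worse: 90 / 21,162 = 0.4%. An example is (3,3,3) to (4,4,2): count 9 to 10, score 1.00 to (1+1+2)/3 = 1.33. Every such case is a net gain of exactly one gland with a worsening of one third of a grade, and at least one zone loses glands. If no zone loses a gland, the score never worsens.

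Over the 216 patterns the score and the count correlate at about -0.97.

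**Effect on power (assumed inputs, none from the documents).** 30 participants; log-odds effect 0.45 on one side; binomial(5, p) per zone; logit SDs of 0.8 between persons, 0.1 to 0.6 between eye-visits and 0.3 between zones; baseline logit -1, 0 or 0.7; paired t-test; 10,000 simulated trials per scenario. Relative efficiency is the squared ratio of standardised effects, mean grade over count.
- Relative efficiency: about 0.83-0.92.
- Power loss: about 3-8 percentage points. Examples are 0.72 with the count against 0.66 with the mean grade at eye-visit SD 0.3, and 0.48 against 0.45 at eye-visit SD 0.6.

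**The case against.** The strongest reply is that this is a measurement preference. The scale is published and cited, and other ordinal grades in the plan (Oxford staining, meiboscale, lid wiper epitheliopathy) coarsen their measurements too. The score follows the count closely, the 40% figure weights all patterns equally, and nothing in the documents shows that a one-gland change exceeds grading noise. The power figures rest on chosen inputs and on a model without counting error, which favours the count. All of this stands, and it limits the point to a gain in precision.

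Three stronger readings are tempting, and the documents support none of them.
- A reader might infer that the exact count is needed to assign the grade and so is already in hand. The bands require telling 0, 1-2, 3-4 and 5 apart. They never require telling 1 from 2 or 3 from 4, and the plan does not say that counts were kept. The most one can say is that the count is obtainable from the same expression.
- A reader might infer that the score commonly points the wrong way. Reversals are 0.4% of pairs, always one net gland, and occur only when a zone loses glands. Whether such a shift is an improvement is itself arguable.
- A reader might infer that the trial's conclusions are compromised. No primary outcome is named, so the weight of this score cannot be judged.

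The objection does not remove the main point: the same examination can yield a finer measure that suits the planned tests better, while the published grade is kept.

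**Conclusion.** The point holds as a cheap improvement, not as a fault that invalidates the plan. That 40% of one-gland gains go unseen, and that scores from 1.00 to 2.00 each cover counts three glands apart, follows from the section 2.v bands once the score is read as the mean of three zone grades; the 40% also assumes equal weight for every pattern. The efficiency of 0.83-0.92 is equivalent to losing roughly 8-17% of participants for this outcome (1 - 0.92 = 0.08; 1 - 0.83 = 0.17). It is illustrative only, because sample size, effect and variances were all assumed. Reversals are a minor point. The point concerns expressibility alone; this arithmetic does not apply to the meibum quality scale.

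**What to change.** - In section 2.v, state that the number of expressing glands is recorded for each zone during the existing expression, and that the expressibility outcome is the total per eye (0-15, higher is better).
- Use that total in the planned repeated measures ANOVA and within-visit paired tests.
- Keep the published grade as a supportive analysis, described as the mean of three zone grades.

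Cost: no new procedure or equipment, only three recorded numbers per eye and visit and a short text change. Direct comparability with papers that report the grade is slightly reduced, which the supportive analysis largely covers.

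The documents are written in the past tense, so data may already have been collected. If zone counts were recorded, the count analysis can be added but must be labelled post hoc. If only grades were stored, the counts cannot be recovered. The report should then describe the score as the mean of three zone grades and state its coarseness as a limitation.

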**vi. Oculus Keratograph 5M, Part 2**

This instrument was also used for imaging sodium fluorescein and Lissamine green staining, graded using the Oxford scale (from 0, absent to 5, severe) for the overall cornea and bulbar conjunctiva [10]. For each participant, a fluorescein sodium impregnated dry strip (Bio Fluoro, Bio-Tech Vision Care, Gujarat India) was moistened with a drop of saline solution (sodium chloride 0.9%), and the excess fluid shaken off, before applying on the lower temporal palpebral conjunctiva after slightly everting the lower eyelid. The same was done with a lissamine green impregnated dry strip (Contacare Ophthalmics and Diagnostics, Gujarat, India), but with the excess fluid allowed to fully coat the whole strip, before a large droplet was instilled in the same manner. Imaging was conducted following this using the in-built blue light and yellow filter, and then the white light for lissamine green staining. Following upper and lower lid eversion, lid wiper epitheliopathy was also assessed by grading the width (0: < 25 %; 1: 25 to 50 %; 2: 50 to 75 %; 3: > 75 %) and length (0: < 2 mm; 1: 2 to 4 mm; 2: 5 to 9 mm; 3: > 10 mm) of the staining [11], and an average of the width and length grading taken as the lid wiper epitheliopathy grading for each of the upper and lower eyelid. Meibography of the upper and lower lids were performed and graded using the meiboscale for the percentage area of gland loss or atrophy compared to the whole tarsal area (0: around 0%; 1:  $\leq 25\%$ ; 2: 26 to 50%; 3: 51 to 75%; 4:  $> 75\%$ ) [12].

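### Is the meibum quality score undefined because the printed scale has no grade for a gland that expresses nothing?

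*Combined protocol and SAP*

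**What the plan says.** Section v describes diagnostic expression of 15 glands: five temporal, five central, five nasal. Expressibility is graded by the number of glands out of five that yield anything: "0: all 5 glands expressing; 1: 3 to 4 glands; 2: 1 to 2 glands; 3: no glands expressing". Quality is graded on the "Bron scale (0: clear fluid; 1: cloudy fluid; 2: cloudy particulate fluid; 3: inspissated". One closing phrase covers both: the grades are "averaged across the 15 glands assessed". The scales are attributed to a cited workshop report on diagnosis of the condition; the section prints the grade labels and no further scoring rules.

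Table 2 lists "Meibomian gland expression with Korb expressor" under slit lamp biomicroscopy, which is ticked at all six visits. For the analysis, the Statistical Analysis section states: "Two-factor repeated measures analysis of variance (ANOVA) was used for statistical analysis to assess changes over time across the multiple visits". Paired tests are also "used to assess differences between the two treatment modalities within the same visit". It has no rule for ungradable or missing values.

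**The concern.** Grades 1 to 3 of the expressibility scale each imply at least one gland in the five with no output. All four quality grades describe a secretion. Read literally, a mean over 15 glands needs 15 numbers, and the printed quality scale supplies one only for a gland that expresses. The trial treats Meibomian gland dysfunction, so non-expressing glands are to be expected.

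The design makes this look worse. Sham IPL is given on the contralateral side, so the treatment contrast is between two sides of one face. If one treatment opens more glands, the handling of non-expressing glands enters that contrast and need not cancel. A side with no expressing gland could score best, worst or nothing at all. If it scored nothing, one of the participant's 2 sides x 6 visits = 12 values would be missing, and a complete-case repeated measures ANOVA (an assumption) would drop the participant.

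**Working it through.** The plan gives no numerical result, sample size or frequency of non-expression for this measure, so there is no figure to reproduce. The check has three parts: how far the convention could matter, which conventions the text allows, and what a change would gain.

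**1. How far it could matter.** From section v: 15 glands, quality grades 0 to 3. Assumed: n = 6 glands express at grade m = 1; later k = 6 more express, all at grade g.

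- Left out: change = k(g - m)/(n + k) = 6(g - 1)/12 = 0.5(g - 1)
- Scored 0: change = kg/15 = 6g/15 = 0.4g
- Scored 3: change = k(g - 3)/15 = 6(g - 3)/15 = 0.4(g - 3)

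| Convention | Start | g = 0 | g = 1 | g = 2 | g = 3 |
|---|---|---|---|---|---|
| Left out | 6/6 = 1.0 | -0.5 | 0.0 | +0.5 | +1.0 |
| Scored 0 | 6/15 = 0.4 | 0.0 | +0.4 | +0.8 | +1.2 |
| Scored 3 | (6 + 27)/15 = 2.2 | -1.2 | -0.8 | -0.4 | 0.0 |

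With no expressing gland the mean is 0/0, 0/15 = 0.0 or 45/15 = 3.0. With all 15 expressing, the three agree. At g = 1 or 2 the sign depends on the convention.

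**2. Which conventions fit the text.**

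- *Left out.* The divisor would be the number of expressing glands, whereas the text averages over the 15 assessed. The 0/0 case and the lost participant arise only here.
- *Scored 0.* A grader would have to record clear fluid, the best grade, where no fluid was seen. Nothing suggests this.
- *Scored 3.* This keeps 15 as the divisor and gives the gland the worst grade, as the expressibility scale does for a zone with no output. It is inference, not text, but it fits best. In the table's last row the change lies between -1.2 and 0.0, and opening a gland never counts as worsening.

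The calculation also assumes a quality grade for each gland. Expressibility is graded per five glands, so its average is naturally a mean of three zone grades. If quality was graded the same way, only a zone with no expressing gland lacks a grade, and the six-gland illustration does not describe the score.

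**3. What a change would gain.** Expressibility is graded on the same glands at the same visits, and obstructed orifices are counted, so a quality mean shifted by gland opening can be read against both. A mean among expressing glands would compare different sets of glands between visits and sides, chosen by a state that treatment may alter. A count of glands with clear fluid ignores glands that open to cloudy fluid: above it goes from 0 to 6 if g = 0 and stays at 0 otherwise. That count and a sensitivity analysis both need gland-level records, which the plan does not say were kept.

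**Lid-wiper bins.** Section vi has similar loose edges. In "width (0: < 25 %; 1: 25 to 50 %; 2: 50 to 75 %; 3: > 75" percent, exactly 50% falls in two grades. In "length (0: < 2 mm; 1: 2 to 4 mm; 2: 5 to 9 mm; 3: > 10 mm", exactly 10 mm falls in none, nor do readings between 4 and 5 or 9 and 10 mm unless whole millimetres are recorded. Width and length grades are averaged, so one unresolved edge moves the score by 1/2 = 0.5 on a 0 to 3 scale. Nothing ties edge readings to one treatment, so this is grading noise.

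**The case for a change.** The best case for a change is that the gap lies inside one sentence, the missing category is foreseeable in this disease, and the convention can alter the direction of a between-side difference. Inspissated describes thickened material, not its absence, so grade 3 cannot be assumed to cover a non-expressing gland. The cited report may hold the rule, but it is not restated and cannot be checked here. Grading by zone does not close the gap either, since a zone with no output still has no printed quality grade.

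Most of this stands as a remark on completeness: a reader of the results needs to know the convention. It does not show that the score lacks a definition in use. The reversal of sign needs at least one of the two conventions that fit the text poorly, and every gland count behind it is assumed. The text is written in the past tense, so the graders have already met the case and settled it. Naming their convention belongs in the report of results and alters neither measurement nor analysis.

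**Conclusion.** No change to the plan. The omission is real, but it is a gap that graders and analysts fill sensibly. The convention that best fits the printed text gives illustrated changes of -1.2 to 0.0 with no reversal of sign. The wider spread, from -1.2 to +1.2 across all three conventions, rests on assumed gland counts and on two readings the text does not favour. The loss of a participant rests further on an assumed complete-case fit.

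The measure is one of many in Table 2, the documents name no primary outcome, and no sample size or error rate depends on it. The conclusion assumes that one convention was used on both sides and at all visits. A convention that differed between sides would be a serious matter, but nothing in the documents points to one.
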